| Population Studied | 60 patients referred or seen at the UCLA clinic Inclusion criteria: 1) | | | |
| | likely a lacunar stroke syndrome within the past 6 months, 2) age | | | |
| | 40-above, 3) absence of signs or symptoms of cortical dysfunction, | | | |
| | 4)MRI presence of a small subcortical ischemic, 5) white matter | | | |
| | hyperintensity score of 2 (moderate) or 3 (severe) on the European | | | |
| | Scale of Age-Related White Matter Change. | | | |
| | Randomized Phase: Medical (control) or Remote Ischemic | | | |
| | PreConditioning (RPreC) | | | |
| Device | Automated Remote Ischemic Conditioning (autoRIC TM) device and | | | |
| | cuffs | | | |
| Number of Subject | 3 | | | |
| Enrolled | | | | |
| Number of Devices | 6 | | | |
| Shipped | | | | |

A. Specific Aims

The general aim of Remote Preconditioning Over Time to Empower Cerebral Tissue (REM-PROTECT) is to evaluate remote limb ischemic preconditioning (RPreC) as a novel therapeutic strategy to prevent stroke, progressive ischemic brain injury, and cognitive decline in patients with moderate to severe cerebral small vessel ischemic disease. A single site, feasibility doseranging randomized clinical trial of RPreC will be performed.

This is a feasibility early phase device trial to determine the feasibility of therapy adherence during chronic use before going to larger trial. Long-term compliance with this treatment with some nuisance aspects in a US small vessel stroke population is unknown and this fundamental piece of

information is needed to plan any subsequent trial. We want to test this technology and hope to achieve a goal of at least 75% or more compliance for physiologic targets.

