During periods of active treatment, RPreC will be induced twice a day by using the autoRIC[™] device (which delivers four remote ischemic conditioning cycles of five minute intervals followed by five-minutes of normal blood flow) around both upper body extremities. The RPreC intervention will be add-on therapy to guideline-based best standard medical prevention therapy. The study will have a randomized phase and a follow-up phase. 60 enrolled patients will be randomized 2:1 to best standard medical care plus active RPreC for 1 year and then follow-up for 1 year versus best standard medical care alone for 1 year and then active RPreC for 1 year. Primary outcome measures will be obtained at the end of the first randomized year (staggered start RCT design). Successful completion of this trial will delineate the feasibility and safety, and explore biomarker indicators of potential efficacy, of inducing brain ischemic tolerance in small vessel stroke-prone patients.

A.1. Specific Aim 1: Feasibility

To establish the feasibility of remote ischemic preconditioning as a sustained therapy for prevention of ischemic brain injury from cerebral small vessel disease.

This aim will be accomplished by demonstrating the remote ischemic preconditioning treatment can be successfully implemented with more than 75% adherence among enrolled patients throughout the 1-year of active treatment. Both patient self-report and remote physiologic monitoring will be performed to quantify patient behavioral adherence to the treatment regimen, and remote physiologic monitoring will be used to quantify physiologic attainment of brief ischemia states in the upper extremities. Establishment of feasibility will allow for subsequent larger, definitive clinical trials of RPreC as a treatment to confer long-term protection against ischemic brain injury due to cerebral small vessel disease.

A.2. Specific Aim 2: Safety

To determine the safety of remote ischemic preconditioning as a sustained therapy for prevention of ischemic brain injury from cerebral small vessel disease.

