In this study, the device will be used with Applicator Cuffs bilaterally for 12 months to provide ischemic preconditioning therapy to the patient's upper extremities. The applicator cuffs are available in three different adult sizes according to the SP10 standard (small, medium or large) and the cuff is selected to match the arm size of the patient. To assure a total cessation of blood flow

through the limb during the ischemic duration, the cuff inflation pressure is maintained at 200 mm Hg. By Doppler ultrasound, it has been documented that inflation of the blood pressure cuff to 200mm Hg causes cessation of blood flow in the arm^{1,2}. A total of four (4) inflation and deflation cycles will be applied in five (5) minute intervals twice a day. At the end of this automated process, the Procedure Complete indicator is illuminated and an audible tone is heard. The autoRICTM will be used for 12 months to deliver remote ischemic conditioning to the patient. There have been no reported experiences of any side effects in preclinical and clinical studies.

In addition to the autoRIC® Device, CellAegis Devices, Inc. developed the CRICtrac[™] Mobile Application that allows the clinician and coordinators to monitor compliance of each individual study participant. Once the patient has been assigned to a treatment group, the coordinator will initialize new patient cuffs by scanning them using the CRICtrac[™] Mobile App on a compatible Android smartphone equipped with a near-field antenna utilizing a Wi-Fi network connection. During the course of the trial or at the end of the trial, patient compliance can be monitored using the CRICtrac[™] Data Portal providing that the cuff has been scanned. The compliance data is immediately uploaded to the CRICtrac[™] Data Portal. The Data Portal can then be accessed via a link from the Mobile App or on any device with internet access. Once logged in, Trial Coordinators can view and/or export patient and trial information.

C2.1. Device Training

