- 14. Pre-existing neurologic, psychiatric, or advanced systemic disease that would confound the neurological or functional outcome evaluations
- 15. SBP <90 or > 200
- 16. Known history of limb vascular disease, limb vascular bypass surgery, or limb deep venous thrombosis
- 17. All women status post mastectomy (standard-of-care re: blood pressure proscription ipsilateral to prior mastectomy)
- 18. Patients with a contraindication to taking blood pressure in the arm for any reason;
- 19. Patients with a known bleeding disorder or known abnormality of blood flow to the limb.
- 20. Patients with osteoporosis or other bone disorders
- 21. Patients with peripheral nerve injury
- 22. Patients with abnormal nerve supply
- 23. Patients with peripheral neuropathy
- 24. Patients with pre-existing traumatic injury to the limb.
- 25. Prisoners
- 26. Homeless individuals
- 27. Patient unable to give informed consent and no available legally authorized representative to provide informed consent
- 28. Patient unlikely to be compliant with therapy/ unwilling to return for follow up visits
- 29. Concurrent participation in another study with investigational drug or device treatment
- 30. Other likely specific cause of stroke (e.g. dissection, vasculitis, prothrombotic diathesis, drug abuse)

C.4. Enrollment and Consent

After initial patient contact and assessment, the physician-investigator will review the patient's relevant medical history and will verify the diagnosis of small subcortical stroke and moderate to severe WMH and determine eligibility for study entry according to inclusion and exclusion criteria above. Study participants who are competent or who have a legally authorized representative will be enrolled.

C.6. Study Treatment

Randomized Phase: Following signing of the consent form, the patient will be randomized and depending on randomization receive treatment with RPreC once daily, twice daily, or none for 1 year. The RPreC procedure will consist of up to four 5-minute cycles of bilateral upper extremity ischemia, separated by 5-minute periods of reperfusion. Primary outcome measures will be obtained at 1 year.

Follow-up Phase: Patients assigned to RPreC in the first year will exit the trial at the end of Year 1. In contrast, patients assigned to the control arm in the first year will at the start of Year 2 enter a staggered therapy start phase, receiving active RPreC for 1 year (randomized 10 to once daily

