Following the randomization assignment, all patients will have follow-up visits at 1, 3, 6, 9, and 12 months. Feasibility, safety, and efficacy assessments will be performed at each of these visits, with the 12 month measures, at the conclusion of the randomized phase, constituting the primary outcome timepoint. In addition, the 20 control patients will have follow-up visits at 18 and 24 months, during the period of their delayed start therapy. The cognitive assessment battery will be performed at the first qualifying visit to familiarize participants with the system before the baseline assessment at randomization and additionally at 1 month to assess whether any cognitive changes accompanied the initial RPreC effect. If participants ceased study treatment during the study, they will be encouraged to continue attending follow-up visits; all withdrawn participants will be invited to attend the closeout visit to reduce loss to follow-up.

C.10. Treatment Evaluation

C.10.1. Baseline Evaluation

At study entry, enrolling investigator to record:

- Demographic data (age, sex, vascular risk factors)
- Heart rate
- Blood pressure
- Visual inspection of skin in arms, motor and sensory examinations of the hand
- NIH Stroke Scale (NIHSS)
- Modified Rankin Scale (mRS)
- Barthel Index (BI)
- EQ-5D (health-related quality of life)
- Questionaire to verify stroke free status
- Neurocognitive battery
- MR imaging will be reviewed
- Eligibility for enrollment
- Review informed consent with patient

C. 10.2. Day 30 Evaluation

- Interval Events Form
- Concomitant therapies form
- Heart rate
- Blood pressure
- Visual inspection of skin in arms, motor and sensory examinations of the hand
- NIH Stroke Scale (NIHSS)
- Modified Rankin Scale (mRS)
- Barthel Index (BI)
- EQ-5D (health-related quality of life)
- Questionaire to verify stroke free status

- Patient-reported Comfort Rating Scale a 5 point Likert scale reflecting patient report of subjective experience of RPreC (very comfortable, comfortable, average, uncomfortable, very uncomfortable) (Wang X, Maurin M. Discomfort/Comfort assessment using an ordered category scale.)
- Number of completed 5-minute cycles of RIPC
- Neurocognitive battery

C. 10.3. Month 3, 6, and 9 Evaluations

- Interval Events Form
- Concomitant therapies form
- Heart rate
- Blood pressure
- Visual inspection of skin in arms, motor and sensory examinations of the hand
- NIH Stroke Scale (NIHSS)
- Modified Rankin Scale (mRS)
- Barthel Index (BI)

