Feasibility: Because the primary aim of this trial is assessing feasibility and tolerability, the primary endpoints are descriptive statistics describing the implementation of the RPreC procedure, including behavioral adherence to treatment, physiologic attainment of limb ischemia, and patient self-reported comfort-discomfort during treatment. The simplicity of these endpoints reduces the likelihood of problems in the analysis and interpretation of these endpoints. The procedure will be considered adequately feasible if adherence and physiologic targets are attained in 75% or more of cases. At this early stage of development, observations and lessons from individual cases may warrant procedural protocol changes to optimize the intervention. Such flexible, developmental iterations of the intervention will be closely discussed with, and supervised by, the study DSMB.

Safety: The lead safety endpoint will be all serious adverse events. Secondary safety endpoints will be deep and superficial vein thrombosis and all cause mortality.

Efficacy: The lead efficacy endpoint will be volumetric progression of white matter ischemic injury on magnetic resonance imaging (biomarker efficacy). The primary MRI endpoint will be the proportion of patients with increase in total white matter hyperintensity volume (as percent of total brain volume) above 1.0%. (This value represents the threshold for the upper quintile of progression in the SCOPE trial. Proportion of patients with progression in the upper quintile was the most sensitive MR endpoint analyzed in the SCOPE substudy.) Additional MRI endpoints analyzed will include mean progression total white matter hyperintensity, mean and quintile progression in deep white matter hyperintensity, progression in total brain atrophy, and progression in DTI anisotropy. The MR imaging measures of white matter injury progression, ascertained by automated analysis and blinded readers, are not subject to bias.

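### C.14.3 makes feasibility depend on adherence and an undefined physiologic target, while A.1 and C.14.4 rest it on adherence alone, the only rule the power table covers

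*Combined protocol and SAP*

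**What the plan says.** **The success rule.** C.14.3 describes the primary endpoints as descriptive, "including behavioral adherence to treatment, physiologic attainment of limb ischemia, and patient self-reported comfort-discomfort during treatment", and then sets a pass mark: "The procedure will be considered adequately feasible if adherence and physiologic targets are attained in 75% or more of cases". Section A likewise expresses the "hope to achieve a goal of at least 75% or more compliance for physiologic targets".

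**Other statements of success.** A.1 ties the feasibility aim to more than 75% adherence over the year of active treatment. C.11 gives the primary endpoint as tolerability and adherence in the intervention arms. C.14.4 gives it as adherence at 12 months and tests it one-sided against 75%. None of the three makes a physiologic target part of the pass mark.

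**Measurement.** A.1 states that "remote physiologic monitoring will be used to quantify physiologic attainment of brief ischemia states in the upper extremities". C.2 describes a mobile app and data portal that "allows the clinician and coordinators to monitor compliance of each individual study participant". The follow-up visit lists in C.10 record comfort, skin, motor and sensory checks, and "Number of completed 5-minute cycles of RIPC". They list no measure of limb flow or occlusion.

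**Cuff pressure and entry limit.** C.2 gives 200 mmHg as the inflation pressure, chosen "To assure a total cessation of blood flow", and supports it with earlier Doppler findings. Exclusion 15 in C.3.1 reads "SBP <90 or > 200".

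**The concern.** The trial exists to give a go/no-go answer on feasibility for a larger successor. If adherence reaches the mark and physiologic attainment does not, or cannot be determined, A.1 and C.14.4 say feasible while C.14.3 says not feasible or gives no answer.

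The physiologic half has a named method but no signal, threshold, schedule or definition of a case that meets it. Two analysts could not be expected to classify the same patient the same way. Nor does the plan say whether both targets must be met in the same patient or whether each must separately reach 75%.

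A reader who takes the C.14.4 power figures as the chance of passing the C.14.3 rule would be using figures computed for a different rule.

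**Working it through.** **Inputs from the documents.** Null value 0.75, one-sided; alpha 0.10 or 0.05; true adherence 90% or 95%; N = 20, 40 or 60 (C.14.4). There are 40 patients on active treatment in Year 1 (C.3).

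**Inputs assumed.** The documents give no physiologic attainment rate. I use 90% and 95% for illustration.

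**Step 1: reproduce the table.** The exact binomial cut-off r is the smallest count with P(X ≥ r | N, 0.75) ≤ alpha; power is P(X ≥ r | N, p). For N=40 and alpha 0.05, P(X ≥ 35 | 0.75) = 0.043 and P(X ≥ 34 | 0.75) = 0.096, so r = 35.

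| N | alpha | r | Power at 90% (stated) | Power at 95% (stated) |
|---|---|---|---|---|
| 20 | 0.05 | 19 | 0.392 (0.392) | 0.736 (0.736) |
| 40 | 0.10 | 34 | 0.9005 (0.901) | 0.997 (0.997) |
| 40 | 0.05 | 35 | 0.794 (0.794) | 0.986 (0.986) |
| 60 | 0.05 | 51 | 0.927 (0.927) | 0.999 (0.999) |

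The remaining power cells reproduce too. The table is right for adherence.

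**Step 2: per-patient joint rule, C.14.4 cut-off.** Let a be the adherence rate and b the physiologic rate. The joint rate lies between a + b − 1 and min(a, b), and equals a × b under independence. It can never exceed a, so at a fixed cut-off the adherence power is an upper limit. For N=40, alpha 0.05, r = 35 and a = 0.90:

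| b (assumed) | Joint rate | Power |
|---|---|---|
| 100% | 0.900 | 0.794 |
| 95%, independent | 0.90 × 0.95 = 0.855 | 0.468 |
| 90%, independent | 0.90 × 0.90 = 0.810 | 0.202 |
| 90%, any dependence | 0.80 to 0.90 | 0.161 to 0.794 |

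**Step 3: two separate tests, both must pass.** With independence at 90% and 90%, power is 0.794 × 0.794 = 0.630. At 90% and 95% it is 0.794 × 0.986 = 0.783.

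**Step 4: C.14.3 read literally, as an observed 75%.** The mark is 0.75 × 40 = 30 patients.

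| True joint rate | P(X ≥ 30 of 40) |
|---|---|
| 75% | 0.58 |
| 80% | 0.84 |
| 81% | 0.88 |
| 90% | 0.999 |

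This mark is five patients below the tested cut-off of 35, so the observed-proportion rule and the C.14.4 test are also different rules.

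**The case against.** The strongest reply has four parts.

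- **The plan does provide for measurement.** A reader might infer from C.2 and C.10 that nothing in the plan measures ischaemia and that half the rule has no data behind it. The documents do not support that: A.1 commits to remote physiologic monitoring for this purpose. What stands is that the commitment is not carried into C.2, C.10 or C.14.3 as a target, a signal or a per-case rule.
- **The table never claims to cover a joint rule.** This is correct; C.14.4 is labelled as adherence. The defect is that C.14.3 and C.14.4 state different success rules, not that the table is miscalculated.
- **The low power figures are only one reading.** A reader might infer that the trial has about 20% power for its primary rule. That needs a per-patient joint reading, the 35-of-40 cut-off, an assumed 90% physiologic rate and independence. Ischaemia can be attained only in sessions that are performed, so positive dependence is likely. The 0.161 end requires that no patient fails both targets, which is implausible. Under the literal observed rule the pass probability is high.
- **The cuff pressure is supported.** C.2 cites Doppler evidence at 200 mmHg, and no eligible patient enters with a systolic pressure above that. A reader might infer that the protocol's figures show completed inflations fail to produce ischaemia. They do not; they show only that no margin is left at the boundary, and no pressure distribution is given to size it.

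That the endpoints are called descriptive does not remove the point: C.14.3 still sets a pass mark, and C.14.4 still tests a hypothesis at 75%.

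**Conclusion.** The concern holds in limited form. The plan states conflicting primary success rules that can lead to different conclusions, and the stated power belongs to only one of them. The physiologic component is named but not operational, so the joint rule cannot be applied reproducibly as written.

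The size depends on which reading was meant. With 90% adherence, N=40 and alpha 0.05, the stated 0.794 is an upper limit for any rule that adds the physiologic target at the tested cut-off; the illustrative values in Steps 2 and 3 run from 0.202 to 0.783 under independence. The literal observed rule errs the other way: it passes more than half the time when the true rate is exactly 75%. All physiologic rates are assumptions, so these figures show how much the choice of rule matters and do not forecast this trial's power.

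**What to change.** 1. Align C.14.3 with A.1 and C.14.4: base pass/fail on adherence, tested as in C.14.4, and state the cut-off.
2. Report the physiologic component as a separate descriptive endpoint. Label completed inflations as treatment delivered, not as ischaemia attained.
3. If the joint rule is kept, state whether the targets apply per patient or separately, define the physiologic target and its data source, and say that the power table applies to adherence only and gives an upper limit.
4. Reconcile the C.2 statement that 200 mmHg assures cessation of flow with the systolic entry limit of 200 in Exclusion 15.

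Items 1 and 2 are wording changes and need no new procedure. They do change the primary pass rule: the go/no-go claim narrows to treatment delivered, and the 75% goal for physiologic targets in section A would have to be reworded to match. Item 3 keeps the broader claim, but the sponsor must then specify the monitoring that A.1 promises.

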Additional efficacy endpoints explored will include accelerometer assessment of gait quantity and quality in real-world activity; z scores on individual tests and summed performance on the cognitive battery, and incident ischemic stroke, transient ischemic attack, hemorrhagic stroke, myocardial infarction, and cardiovascular death. To protect against bias in ascertainment of the recurrent stroke secondary endpoint, analysis to include a) adjudication of potential endpoint stroke events by 2 independent blinded neurologists (preventing rater bias), and b) administration of the Questionnaire to Verify Stroke Free Status at each follow-up visit, to trigger endpoint evaluations (preventing ascertainment bias).

C.14.4. Sample Size Calculations

Subject size is typical sample size for a feasibility study with a device. We are looking at adherence in order to plan a larger phase II/III successor trial.

Sample Size Justification

The primary feasibility and study endpoint is RPreC adherence at 12 months. As we do not expect clinically important differences in adherence among the three groups, it may be possible to combine two or all three groups. In this study, we also wish to test the null hypothesis that the true adherence is at least 75%. The table below gives the lower 90% or 95% confidence bound for 90%, 95% or 100% observed adherence as a function of sample size and the corresponding statistical power for testing the null hypothesis that the true population adherence is 75% versus the one sided alternative of greater than 75%. The current study is not necessarily sufficiently powered for any of the safety or efficacy outcomes. Therefore this is a pilot study in terms of safety and efficacy.

Lower 90% or 95% one sided confidence bound for true adherence

| | adherence=90% | | adherence=95% | | adherence=100% | |
|----|---------------|------------|---------------|------------|----------------|----------------|
| | 90% | 95% | 90% | 95% | | |
| Ν | confidence | confidence | confidence | confidence | 90% confidence | 95% confidence |
| 20 | 75.5% | 71.8% | 81.9% | 78.5% | 89.1% | 86.1% |
| 40 | 81.0% | 78.5% | 87.2% | 85.1% | 94.4% | 92.8% |
| 60 | 83.1% | 81.2% | 89.2% | 87.6% | 96.2% | 95.1% |

Power for one sided test against null hypothesis of 75% vs > 75%

| | adherence=90% | | adherence=95% | | adherence=100% | |
|----|---------------|------------|---------------|------------|----------------|------------|

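### The 75% feasibility criterion is stated in several incompatible forms, and the per-patient adherence status that the power table needs is never defined

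*Combined protocol and SAP*

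**What the plan says.** The 75% figure appears in four places.

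- **Section A, opening:** "We want to test this technology and hope to achieve a goal of at least 75% or more compliance for physiologic targets".
- **A.1:** success is "more than 75% adherence among enrolled patients throughout the 1-year of active treatment". The data sources are given as "Both patient self-report and remote physiologic monitoring will be performed to quantify patient behavioral adherence to the treatment regimen".
- **C.14.3:** "The procedure will be considered adequately feasible if adherence and physiologic targets are attained in 75% or more of cases". The same paragraph calls the primary endpoints descriptive and lists three: behavioral adherence, physiologic attainment and comfort.
- **C.14.4:** "The primary feasibility and study endpoint is RPreC adherence at 12 months". Tables of one-sided lower bounds and power follow for N = 20, 40 and 60. The text words the null as a true adherence of 75% or higher; the power table tests 75% against more than 75%.

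The visit schedules in C.10 record a count: "Number of completed 5-minute cycles of RIPC". On the regimen, C.6 says "The RPreC procedure will consist of up to four 5-minute cycles of bilateral upper extremity ischemia", while A and C.2 say four cycles. A and C.2 describe twice-daily use only, while C.1 and C.6 have once-daily and twice-daily arms.

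**The concern.** Adherence is the endpoint for which the plan gives power, and its result is meant to decide whether a larger trial goes ahead. The four statements differ in the quantity (behavioral, physiologic or both), in the threshold (more than 75%, or 75% and above) and in the kind of decision (a descriptive cut-off or a hypothesis test). No section says what makes one patient adherent, whether a case is a patient or a session, or which source decides if self-report and device monitoring disagree. If these choices stay open until data are in hand, the same results could be reported as feasible or not feasible.

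**Working it through.** **1. Reproduce the plan's table.** Inputs from C.14.4: p0 = 0.75, one-sided alpha 0.10 or 0.05, true adherence p1 = 90%, 95% or 100%, N = 20, 40 or 60. Method: find the smallest r with P(X ≥ r | N, 0.75) ≤ alpha; power is P(X ≥ r | N, p1).

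| N | alpha | r | actual size | power at 90%: exact | stated |
|---|---|---|---|---|---|
| 20 | 0.10 | 18 | 0.091 | 0.677 | 0.677 |
| 20 | 0.05 | 19 | 0.024 | 0.392 | 0.392 |
| 40 | 0.10 | 34 | 0.096 | 0.900 | 0.901 |
| 40 | 0.05 | 35 | 0.043 | 0.794 | 0.794 |
| 60 | 0.10 | 50 | 0.086 | 0.966 | 0.966 |
| 60 | 0.05 | 51 | 0.045 | 0.927 | 0.927 |

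The 12 power cells given as numbers agree within 0.001, and the cells given as above 0.99 are also consistent. All 18 lower bounds agree with one-sided Clopper-Pearson limits within 0.1 point. A normal approximation does not fit (N = 20, alpha 0.05, 90%: 0.445 against 0.392). The table is therefore exact binomial, with each patient counted as adherent or not.

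**2. Apply the stated rules to the same count.** Both descriptions of the allocation (2:1 in A and C.3, 1:1:1 in C.1) put 40 patients on device in the randomized year. Reading each rule as a share of patients:

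- 30/40 = 75.0% meets C.14.3 (75% or more) but not A.1 (more than 75%).
- 30 to 33 of 40 (75.0% to 82.5%) meets C.14.3 but does not reject in the C.14.4 test, which needs 34 (85.0%) at alpha 0.10 or 35 (87.5%) at 0.05.
- At a true rate of exactly 75%, C.14.3 passes with probability P(X ≥ 30 | 40, 0.75) = 0.584. The test rejects with probability 0.096 or 0.043.

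This step assumes nothing about how adherence is distributed within patients.

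**3. Mean of sessions against share of patients.** Illustration with assumed values: 28 patients complete 95% of sessions and 12 complete 40%.

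- Mean = (28 × 95 + 12 × 40)/40 = 3140/40 = 78.5%, above 75%.
- Share of patients reaching 75% = 28/40 = 70%, below 75%.

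The 75% per-patient cut is also an assumption; the plan gives none.

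**4. The physiologic component.** Suppose a patient must meet both the adherence and the physiologic target, each has a true rate of 90%, and the two are independent (assumptions). The joint rate is 0.90 × 0.90 = 0.81. At N = 40, P(X ≥ 34 | 0.81) = 0.342 and P(X ≥ 35 | 0.81) = 0.202, against 0.901 and 0.794 in the table.

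**5. The prescribed denominator.** With once-daily and twice-daily arms of 20, assume 90% and 65% of sessions completed. The mean over patients is (90 + 65)/2 = 77.5%. Pooled over sessions, it is (20 × 0.90 + 40 × 0.65)/60 = 44/60 = 73.3%. The regimen and the weighting both matter.

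**The case against.** The strongest reply is that this is a small descriptive feasibility study with one missing sentence, not a set of conflicting definitions. Parts of that stand.

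- A reader might infer that C.14.4 (at 12 months) and A.1 (through the year) conflict on timing. The documents do not require this. C.9 makes month 12, the end of the randomized phase, the primary timepoint, so C.14.4 can mean the year's adherence assessed at month 12. A.1 can also be read as a share of patients.
- A reader might infer that the table fits just one of the definitions. It fits any yes/no status per patient, whether behavioral or physiologic, cumulative or at month 12. It does not fit a mean or a pooled session percentage.
- A reader might infer that mean and patient-level readings generally disagree. They do so near the threshold. Under an assumed beta distribution with SD 15 to 25 points and a 75% cut, a mean of 80% puts about 69% to 70% of patients over the cut. A mean of 85% puts 78% to 79% over it and a mean of 90% puts 86% to 87% over it, so both readings then pass.
- A reader might infer that settling the number of cycles would fix the denominator. It would not, because session frequency also differs between sections.
- C.14.4 calls the sample size typical for a device feasibility study and selects no target power or row.

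The reply does not dispose of step 2. C.14.3 sets a pass/fail rule, C.14.4 sets a test, and the two give opposite verdicts on the same count.

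**Conclusion.** The concern holds and should be fixed before data are seen. The firm part rests on the plan's own figures: 30 of 40 separates C.14.3 from A.1 when both are read as shares of patients, 30 to 33 of 40 separates C.14.3 from the C.14.4 test, and the chance of declaring feasibility at a true 75% is 0.584 under one rule and 0.096 or 0.043 under the other. The power table is arithmetically right, but it describes a per-patient status that the plan does not define. The mean-against-share illustration and the joint-endpoint power (about 0.34 and 0.20) depend on assumed values; they show what could happen and do not predict it.

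**What to change.** - **Definition.** Use one patient-level definition in A.1, C.14.3 and C.14.4, set before data are seen. For example: a patient is adherent if the device log shows that at least 75% of the sessions prescribed for the assigned arm were completed from start of treatment to month 12. The denominator is all patients randomised to device. The 75% per-patient cut is one workable choice; what matters is that a cut is fixed.
- **Decision rule.** State one: either the C.14.4 exact test, with its alpha and its null worded to match the table, or the C.14.3 cut-off with its operating characteristics.
- **Physiologic target.** Say whether it is part of the primary endpoint or a separate criterion. If both are required per patient, restate the power.
- **Secondary reporting.** Report self-reported adherence, mean percent of sessions, and the delayed-start controls. The N = 60 row can be reached only by adding those controls.
- **Regimen.** Reconcile the passages on twice-daily use against once-daily and twice-daily arms, and on up to four against four cycles, so that the prescribed denominator is fixed. No view is taken on which is right.

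The cost is protocol and SAP wording. The existing power table stays valid for a single yes/no status per patient. The downside is that a patient-level rule can be stricter than an average over sessions.
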